Study background (with bibliographic references)	
Kidney transplantation is currently the reference treatment for end-stage kidney disease, with more than 170,000 transplants performed worldwide each year (Global Observatory on Donation and Transplantation, 2024). Despite major progress in short-term survival, long-term graft survival remains limited: approximately 40% of patients return to dialysis within 10 to 15 years after transplantation (Hart et al, AJT 2019, PMID 30838768).
 
In recent years, artificial intelligence (AI) has emerged as a promising tool to predict graft outcomes and support clinical decision-making (Raynaud et al, Lancet Digital Health 2021 PMID 34756569; Loupy et al, Nature Medicine 2025 PMID 40659768). The iBox system, developed by the Paris Institute for Transplantation and Organ Regeneration, makes it possible to calculate a personalized probability of graft loss up to ten years after the evaluation of a kidney transplant recipient.
 
This algorithm has been internationally validated in several cohorts and clinical trials (Lombardi et al, AJT 2025, PMID 39674514; Truchot et al, JASN 2025, PMID 40168162), performs better than clinicians in predicting risk (Divard et al, Communications Medicine 2022, PMID 36418380), and was qualified by the European Medicines Agency as an endpoint for clinical trials in 2022.
 
However, although the clinical value of iBox and similar predictive tools is well documented, how patients perceive them remains largely unexplored.
 
Understanding how kidney transplant recipients perceive the prediction of their individual risk of graft loss (in terms of usefulness, acceptability, fears, or impact on daily life), as well as their broader views on the role of artificial intelligence in medicine, including their hopes, expectations, and concerns regarding its deployment, is essential to ensure implementation that is ethical, transparent, and truly patient-centered (Young et al, Lancet Digital Health 2021, PMID 34446266).

Primary objective and corresponding endpoints (Please specify the longer-term application of the study if necessary)	This study therefore aims to explore the perceptions, expectations, and concerns of kidney transplant recipients regarding the use of artificial intelligence, and to assess their specific perceptions of the use of a graft loss risk prediction system, through an open-ended questionnaire distributed on a large scale in France and the United States.

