	
Data analysis: The responses collected will be analyzed using a quantitative approach. Qualitative analyses will rely on thematic analysis assisted by Large Language Models (LLMs). These models will make it possible to automatically extract recurring themes, associated emotions, and nuances of perception in free-text responses, according to a standardized methodology developed by the investigators' team. The investigators have already successfully conducted this type of LLM-based thematic analysis (Raynaud et al, PsyArxiv 2025 https://osf.io/preprints/psyarxiv/pnx9e_v1).
 
Analyses will be conducted via commercial language-model APIs (Anthropic Claude, OpenAI ChatGPT, xAI Grok), justified by their superior performance for multilingual qualitative analysis. Only pseudonymized text responses will be transmitted, with no identifiers or sociodemographic data. Providers contractually guarantee zero data retention. Participants will be asked not to mention identifying information in their free-text responses (see the information notice in the appendix to this document).
 
To ensure reliability and scientific rigor, systematic manual verification will be performed on a representative subsample of responses. This independent review will make it possible to compare human and automated coding and refine the thematic categories.
 
Originality of the study: Unlike the vast majority of surveys conducted with patients, the questionnaire will contain only open-ended questions, giving each patient the opportunity to express themselves freely and in a nuanced way about their perceptions and feelings.
 
Such an approach, previously difficult to implement on a large scale, is now made possible by language models (LLMs), which are able to finely analyze large sets of textual responses.
 
This innovative methodology will provide a more faithful, precise, and human understanding of patients' perspectives, paving the way for a new generation of studies centered on patients' lived experience and voice.

Data collected (Justify the collection of sensitive/identifying data, if applicable)
	
 • Age • Sex • Year of the last transplant • Country of the last transplant • Transplant follow-up center • Transplant rank • Current occupation or last occupation held • Perceptions of the role of AI in medicine • Perceptions regarding a graft loss risk prediction system

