The prediction system was developed to help physicians and patients assess the health of the kidney graft. It combines several clinical data points (kidney function, histological results, and immunological results) and predicts the percentage of risk that a patient will lose their graft over the next 10 years. The goal of this prediction system is to improve clinical decision-making, as well as the discussion between the physician and the patient.

A. Have you ever heard of this type of prediction system?

B. If yes, does your physician use such a prediction system in your post-transplant follow-up? Do you have access to the predictions?

4. Questions specific to the prediction system

- A. What do you think of the idea that an artificial intelligence such as this prediction system could predict your personal risk of graft loss?
- B. Do you find it useful for your physician to have access to this information? Why?
- C. Would you personally want to know your graft loss prediction?
- D. What fears or concerns do you have about AI being used to predict the outcome of your transplant?
- E. How could this information influence your daily life, for example your personal, family, professional choices, or your leisure activities?

5. General questions about artificial intelligence in healthcare

- A. In general, what do you think about the use of artificial intelligence in today's healthcare?
- B. What hopes or expectations do you have regarding AI in healthcare?
- C. What fears or reservations do you have regarding AI in healthcare?
- D. In your opinion, in what situations should or should not AI be used?
- E. Would you like to add any comments about your feelings regarding this prediction system or AI in medicine?

6. General information (demographics)

Age: _____ (years)

Sex: ☐ Female ☐ Male

Year of last transplant: _____

Country of transplant: _____

Transplant follow-up center: _____

Transplant rank: ☐ First ☐ Second ☐ Third or more

Current occupation or last occupation held: _____

7. Our thanks

Thank you for taking the time to share your perspective. Your responses will help us better understand the role that patients wish to give to artificial intelligence in the medicine of tomorrow. Your transplant center (or your patient association) will share the results of the study with you once the analyses are completed.

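### Item 4C, the only question on wanting to know one's own prediction, is in yes/no form and asks for no reason, unlike the parallel item 4B

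*Protocol*

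**What the plan says.** The primary objective in the Protocol includes the aim "to assess their specific perceptions of the use of a graft loss risk prediction system, through an open-ended questionnaire". The study background lists what has to be understood about patients' views of such a prediction: "in terms of usefulness, acceptability, fears, or impact on daily life".

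Under the heading on the originality of the study, the Protocol states that "the questionnaire will contain only open-ended questions, giving each patient the opportunity to express themselves freely and in a nuanced way". The data analysis paragraph plans for language models to "automatically extract recurring themes, associated emotions, and nuances of perception in free-text responses".

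Two items in section 4 of the appended questionnaire deal with access to the prediction. Item 4B, on the physician's access, reads "Do you find it useful for your physician to have access to this information? Why"? Item 4C, on the patient's own access, reads in full "Would you personally want to know your graft loss prediction"? It has no reason prompt and no follow-up.

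**The concern.** 4B and 4C are neighbours and have the same grammatical form. Both can be answered with yes or no. The authors attached a request for reasons to the first and not to the second, so a one-word reply to 4C is a complete answer. Such a reply gives the thematic analysis nothing to work on: no theme, emotion or nuance.

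What is at stake is the account of why patients would or would not want their own number. As the form stands, everyone is asked for reasons about the physician's access and no one is asked for reasons about their own. The two sets of reasons would then arise differently and could not be compared like for like.

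The gap lies in the instrument, so a statistical analysis plan cannot close it. No coding rule recovers a reason that was not requested. The Protocol describes non-traceable identifiers and allows answers to be changed only before final validation, so it offers no route for asking later.

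**Working it through.** The Protocol states no figure on this point, so the check is a reading of every substantive item in questionnaire sections 3 to 5. Three questions were put to each: does it ask about wanting to know one's own prediction, does it ask for the reason, and could it recover that reason indirectly?

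- **3A** asks whether the patient has heard of such systems. It is factual and does not touch the wish to know.
- **3B** applies only after a yes to 3A. It asks about the physician's current use and, of the patient, "Do you have access to the predictions"? That concerns present access, not the wish for it.
- **4A** asks for an opinion on AI predicting the patient's personal risk. Views on knowing the result may appear, but they are not requested.
- **4B** concerns the physician's access, and reasons are requested.
- **4C** concerns the patient's own wish to know, and no reason is requested.
- **4D** asks about fears of AI being used for prediction. A patient may decline to know for reasons unrelated to AI, for example not wanting a prognosis from any source.
- **4E** asks how the information could affect daily life. This comes closest to a reason, but it asks what knowing could change, not why the patient would accept or refuse it.
- **5A to 5D** concern AI in healthcare generally.
- **5E** is a closing invitation to comment, including on feelings about the prediction system.

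Tally for section 4: one of five items (4C) asks about the wish to know. Two of the five (4B and 4C) are in yes/no form, and only 4B asks for reasons. Items 3A and 3B are also closed in form, but they ask about facts, so a missing reason matters less there. 4C asks about an attitude.

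For scale, the Protocol's distribution and response figures imply 10,000 × 0.10 = 1,000 to 20,000 × 0.15 = 3,000 respondents. Let *b* be the share who answer 4C with a bare yes or no. Reasons at 4C itself then come from (1 − *b*) of those respondents. The documents give no value for *b* and nothing on how it differs between patients who would and would not want to know, so neither the size of the gap nor the direction of any selection can be computed.

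**The case against.** The best defence is that 4C is probably a free-text field. The questionnaire prints tick boxes where a closed answer is meant, as for consent, sex and transplant rank, and 4C has none. Respondents can therefore explain themselves there. 4A, 4D, 4E and 5E sit in the same respondent's record, and a 4C answer can be read against them. This stands, and it limits the point. A reader might infer that the reasons for wanting or refusing to know will be missing altogether, and the documents do not support that. The gap is exact only for respondents who give a bare answer and do not explain elsewhere.

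A reader might also infer that the volunteered reasons will over-represent reluctant patients. Nothing in the documents says which group explains itself more readily. If both explain equally often, the mix of reasons is not distorted; if willing patients explain more, the distortion runs the other way. Once reasons are reported separately by answer, the pooled mix no longer matters. What remains is selection within each group, of unknown size.

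Third, the Protocol does not rank the wish to know above its other topics. It lists usefulness, acceptability, fears and daily impact side by side and names no endpoint based on 4C. The study is also described as mixed-methods, and the simple proportion wanting to know is a legitimate result that bare answers still provide. All of this stands.

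Finally, the wording was tested with six French and American recipients, and the French form is not shown. The testing does not remove the visible mismatch between the English 4B and 4C. Whether the French 4C has the same gap is unknown and has to be checked.

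**Conclusion.** The point holds as an inconsistency in the instrument. The only item on wanting to know one's own prediction is in yes/no form without a reason prompt, it differs from its neighbour 4B, and it does not fit the stated open-ended design with thematic analysis. Reasons will be collected incompletely and from self-selected respondents. The size and direction of that selection are unknown, and no figure should be put on them.

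The study remains valid without the change, and no estimate or planned analysis is wrong because of it. The change is still worth making, because it is nearly free before launch and the information cannot be recovered afterwards. The conclusion rests on the English wording shown and on 4C being a free-text field, as its layout suggests.

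**What to change.** Before distribution, extend 4C so that the present question is followed by *Why, or why not?*, in line with 4B. Compare the French form with the English one and make the same addition there if it is missing. In the analysis, report the reasons separately for those who would and those who would not want to know their prediction.

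The cost is a few words in the REDCap form, a translation check, and slightly more time per respondent within a questionnaire announced as taking 15 to 20 minutes.

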
Summary methodology (What statistical analysis strategy, what type of interview, what mode of observation, etc.)
	
Collaboration with transplant centers and patient associations: The investigators' team is highly collaborative and has a broad international network of clinical and patient-association partners in the field of kidney transplantation. This network, built over the course of the investigators' research and previous collaborations, will be mobilized for the present study.
 
The investigators have already obtained preliminary agreement from three French kidney transplant centers, as well as five patient associations (including France Rein and Le Flambeau de la Vie in France, and The Voice of the Patient and the American Association of Kidney Patients in the United States). These partners will play a key role in disseminating the questionnaire to kidney transplant recipients and in representing the patient perspective.
 
Questionnaire development: The questionnaire was developed based on a literature review on patients' perceptions of artificial intelligence and predictive medicine (Erul et al, Cancer Control 2025, PMID 40407404; Fritsch et al, Digital Health 2022, PMID 35983102).
 
The questionnaire was co-designed and tested with six kidney transplant recipients (French and American), allowing us to refine the wording of the questions and validate the bilingual French-English translation. The questionnaire is implemented via the secure REDCap interface (GDPR-compliant). Each participant receives a personal code allowing them to return and modify their responses before final validation (questionnaire presented in the appendix to this document).
 
Questionnaire distribution: Dissemination will take place through partner patient associations and collaborating transplant centers in France and the United States. The questionnaire will be distributed via a secure and anonymous REDCap platform hosted on institutional servers that comply with data protection standards (GDPR). Participants will receive a unique link providing direct access to the online questionnaire. They will be able to respond independently, at their own pace, and may interrupt their participation at any time without justification or consequence.

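### Items 4D, 4E, 5B and 5C give no cue that 'none' is an answer, so a blank on a completed questionnaire cannot be read as no fear, no opinion or refusal

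*Protocol*

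**What the plan says.** The items are in sections 4 and 5 of the questionnaire appended to the protocol:

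- 4D: "What fears or concerns do you have about AI being used to predict the outcome of your transplant"
- 4E: "How could this information influence your daily life, for example your personal, family, professional choices, or your leisure activities"
- 5B: "What hopes or expectations do you have regarding AI in healthcare"
- 5C: "What fears or reservations do you have regarding AI in healthcare"

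None of the four is printed with 'if any', a 'none' option or a way to decline. Tick boxes are printed elsewhere in the form, for consent, sex and transplant rank.

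Under Summary methodology, the protocol presents the free-text format as the originality of the study: "the questionnaire will contain only open-ended questions". Under Data analysis it states: "The responses collected will be analyzed using a quantitative approach". Language models are to extract themes from the text, with a manual check on a subsample. Under Questionnaire distribution, participants "may interrupt their participation at any time without justification or consequence". Under Questionnaire development, each has a personal code "allowing them to return and modify their responses before final validation".

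The protocol does not say whether the items are mandatory in REDCap.

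**The concern.** The primary objective covers perceptions, expectations and concerns, and the background names fears and impact on daily life among the dimensions of interest. Having no fear, no hope or no expected influence is therefore a finding in its own right. The wording of 4D, 5B and 5C takes the fear or hope as given. Item 4E does so more mildly, by asking how rather than whether. A respondent with nothing to report gets no signal that saying so counts as an answer, and leaving the box empty is the easy course.

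That empty box looks the same as one left by a person with no opinion or one who prefers not to say. Neither the language models nor the manual check can interpret it, since there is no text. The Data flow section describes the identifier as non-traceable, so respondents cannot be asked afterwards. The distinction has to be collected by the instrument or it is lost. Any percentage of recipients voicing a fear, hope or influence would then depend partly on how blanks are treated.

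**Working it through.** The protocol states no precision, power or respondent total, so there is no figure of its own to reproduce.

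**Inputs from the protocol (Number of participants).** 10,000 to 20,000 recipients approached; 10% to 15% expected to respond.

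**Assumed inputs, not in the protocol.** Share b of validated questionnaires with the item blank: 5% to 40%. Share p voicing a fear among those who answer, typed 'none' included: 60%, with 50% and 80% as alternatives.

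**Step 1, respondents.** 10,000 × 0.10 = 1,000; 20,000 × 0.15 = 3,000.

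**Step 2, sampling error.** The largest 95% half-width is 1.96 × √(0.25/n): 3.1 points at n = 1,000 and 1.8 points at n = 3,000.

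**Step 3, effect of blanks.** Three readings of the same data:
- blanks left out: p
- blanks counted as no fear (lower bound): p(1 − b)
- blanks counted as fear (upper bound): p(1 − b) + b

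The first two differ by p × b. The bounds are b wide, whatever p is.

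With p = 60%:

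| Blank rate b | Blanks left out | Blanks = no fear | Upper bound | Shift p × b |
|---|---|---|---|---|
| 5% | 60% | 57% | 62% | 3 points |
| 10% | 60% | 54% | 64% | 6 points |
| 20% | 60% | 48% | 68% | 12 points |
| 40% | 60% | 36% | 76% | 24 points |

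At b = 20%, p = 50% gives bounds of 40% to 60% (shift 10 points) and p = 80% gives 64% to 84% (shift 16 points).

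**Step 4, comparison.** At b = 5% and p = 60%, the half-width among those who answer is 3.1 points with 1,000 respondents (950 answers) and 1.8 points with 3,000 (2,850 answers). The 3-point shift is about equal to the first and larger than the second. From roughly 5% blanks upward, the reading of blanks matters about as much as sampling error or more.

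**Step 5, what other data can resolve.** The final validation step can separate abandoned questionnaires from finished ones. Section 6 (demographics) follows 5C, so a form with section 6 filled in and 5C empty points to a skip rather than a break-off. Neither says why the item was skipped.

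**The case against.** The case against has several parts, and much of it stands.

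- **Denominators.** A reader might infer that the quantitative results have no defined denominator. The protocol sets none, but denominators and rules for empty items are commonly left to the statistical analysis plan, which is not shown. Their absence is no finding.
- **Free text accepts 'none'.** A reader might infer that the problem exists whether or not items are mandatory. A typed 'none' is a codable answer, not filler, and if the items were mandatory most of the ambiguity would go. The setting is not described, so the number of blanks is unknown.
- **Other information.** A reader might infer that the data hold nothing to help with blanks. Besides the validation step and section 6, the same person's answers to 4A, 4B, 5A, 5D and 5E may show concerns. This helps with some blanks, but it does not turn an empty 5C into 'no fear'.
- **No such endpoint.** The objective is exploratory. No prevalence of fear is named as an endpoint, and no comparison of tool-specific fears (4D) with general fears (5C) is planned. A reader might infer that rising blanks across the 12 open prompts would distort that comparison. The protocol supports neither the comparison nor the pattern of blanks.
- **Magnitude.** The 60% and the blank rates are assumptions. The 36% to 76% range is a worst case at the highest assumed blank rate, not a forecast.
- **Tested wording.** Six recipients co-designed and tested the questionnaire. The protocol does not say that empty answers were examined.

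The wording of the four items, and the ambiguity of a blank on a validated form, are untouched by these points.

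**Conclusion.** The point holds in a limited form. The four items presuppose a fear, influence or hope and give no cue that 'none' is acceptable. A blank on a finally validated questionnaire therefore cannot be attributed to no fear, no opinion or refusal, and because this is fixed in the instrument, a later analysis plan cannot recover it. The size is unknown because the blank rate is unknown: at an assumed 60% voicing a fear, the shift is 3 points at 5% blanks and 24 points at 40%. If few boxes are left empty, or the items prove mandatory, little is at stake. This is a modest weakness that is worth removing because removal is nearly free now and impossible after distribution, planned for May 2026.

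**What to change.** Before launch, keep 4D, 4E, 5B and 5C open-ended and reword them neutrally in French and English. For 5C, for example: 'What fears or reservations, if any, do you have …? If you have none, please write none; if you have no opinion or prefer not to answer, please write that.' For 4E, ask whether the information would influence daily life and, if so, how.

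In the analysis, count a written 'none' as a substantive result, show written 'no opinion' and 'prefer not to answer' on their own lines, and report true blanks separately. Give percentages both of those who answered the item and of all validated questionnaires.

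Tick boxes are a less suitable remedy: they depart from the deliberate open-ended design, and a label that joins 'none' with 'nothing comes to mind' would again merge no fear with no opinion.

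The cost is four slightly longer questions and their translation. The downside is that a few respondents may write 'none' rather than elaborate.

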
Data flow (What happens to the data from extraction until deletion? Collection software, storage, security of storage media, access, partner recipients or subcontractors, retention period, etc.)
	
Data will be collected through the REDCap platform (HDS-certified hosting on Google Cloud, GDPR-compliant). The questionnaire is anonymous: no nominative data or identifiable medical data will be collected. Each participant will receive a unique link generating a non-traceable alphanumeric identifier.
 
The data flow is as follows:
 
Dissemination: Partner transplant centers and patient associations disseminate the REDCap link to eligible patients.
 
Collection: Participants complete the questionnaire anonymously via REDCap.
 
Export: Pseudonymized data are extracted (CSV format) by authorized members ([name], [name], [name]).
 
Storage: Files are stored in encrypted form on the secure PARCC INSERM U970 server, with access controlled by secure authentication.
 
Qualitative analysis by LLM: Only textual responses (without identifiers, sociodemographic data, or transplant-related information) are transmitted via secure API (HTTPS/TLS) to language-model providers (zero data retention). Results are returned to the PARCC INSERM server. Quantitative analyses are performed locally using R.
 
Archiving: 3 years in the active database, then 20 years in archives, under the responsibility of [name].
 
Fully anonymized datasets may be archived for secondary research purposes or scientific replicability.

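### Questionnaire item 5D asks in one open question where AI should and should not be used, so an answer that only lists situations has no reliably recoverable direction

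*Protocol*

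**What the plan says.** Section 5 of the questionnaire appended to the Protocol has five lettered items on AI in healthcare. Item 5D reads "In your opinion, in what situations should or should not AI be used". Just before it, the favourable and unfavourable sides are asked separately: 5B is "What hopes or expectations do you have regarding AI in healthcare" and 5C is "What fears or reservations do you have regarding AI in healthcare".

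On format, the Protocol's data analysis text states that "the questionnaire will contain only open-ended questions". No sub-item, tick box or other field for direction is shown under 5D.

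On coding, the same text relies on language models to "automatically extract recurring themes, associated emotions, and nuances of perception in free-text responses". The data flow section adds that "Only textual responses (without identifiers, sociodemographic data, or transplant-related information) are transmitted via secure API". As a safeguard, "systematic manual verification will be performed on a representative subsample of responses", so that human and automated coding can be compared and the themes refined. The Protocol states no rule for a 5D answer that names situations without saying which side they belong to.

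**The concern.** Item 5D is double-barrelled, and its two halves are opposites. For most open questions a short answer loses detail but keeps its meaning. Here a short answer can lose the one thing the item asks for: whether the patient accepts or rejects the use named. A reply consisting of the single word surgery could mean that AI belongs there or that it must be kept out.

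5D is the only item that asks patients directly for the limits of AI use, so it bears closely on the stated aim of exploring expectations and concerns. If undirected answers are assigned to a side, some may be recorded as the opposite of what the patient meant. If they are set aside, the item yields less than it could. In both cases the information was not collected. The survey is anonymous and cross-sectional and describes no follow-up contact, so it cannot be recovered later.

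**Working it through.** No formula applies to the point itself; it rests on the wording. The check sets the relevant parts of the Protocol side by side.

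**1. Does the item record direction?** Item 5D names both directions in one sentence and shows no separate prompts. Three kinds of answer are possible:

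| Answer to 5D | Direction recoverable? |
|---|---|
| Yes for reading scans, no for treatment decisions | Yes, from the text |
| Only for diagnosis | Yes, from the text |
| Diagnosis, surgery | No, fits either half |

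Only the third kind is affected.

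**2. Is this how the questionnaire treats opposite views elsewhere?** No. Hopes (5B) and fears (5C) have an item each, so the side an answer belongs to is fixed by where it is written. The same device is not used in 5D.

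**3. Do the stated safeguards resolve it?**
- *Language-model coding.* The model works from the response text. The Protocol does not say whether one person's answers are sent together or item by item. If 5D is coded alone, an undirected list contains nothing from which direction can be read.
- *Manual verification.* It covers a subsample and compares human with automated coding of the same words. Two coders who read the same undirected list the same way will agree whether or not they are right, so good agreement is no evidence that the direction is correct.
- *Pretest.* The questionnaire was tested with six recipients. Nothing is reported about 5D, so the pretest neither clears nor condemns it.
- *Codebook or analysis plan, not shown.* A category for unclear direction would limit miscoding but would not restore the missing information.

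**4. Scale, as an illustration only.** Inputs from the Protocol's section on the number of participants: 10,000 to 20,000 recipients approached and a response rate of 10 to 15%.
- Lowest number of responses: 10,000 × 0.10 = 1,000.
- Highest number of responses: 20,000 × 0.15 = 3,000.

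The share of 5D answers without a direction is not given. Assume, without a source, 5 to 30%, and assume that every respondent answers 5D:
- Low end: 1,000 × 0.05 = 50 answers.
- High end: 3,000 × 0.30 = 900 answers.

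The width of this range shows how little is known. How many of these would be given the wrong direction cannot be derived from the Protocol.

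**The case against.** The strongest reply is that 5D, by naming both directions, invites respondents to say which one they mean, and that open text lets them do so. Many will, and their answers can be coded. This stands, and it limits the point to undirected answers.

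Second, nothing in the Protocol forces a two-way code. An unclear category is ordinary codebook content, and a reviewer on the study side could read 5B and 5C beside 5D to infer the direction. This also stands in part: reversals are possible but not inevitable. However, the Protocol commits to neither step, and neither recovers what the item failed to ask for.

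Third, the single answer box is inferred from the single lettered item. If the REDCap form already has two labelled fields, the point falls away.

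Fourth, a split does not make every blank interpretable. An empty field for unacceptable uses may mean no objection, no opinion or fatigue. That is true of any open question, and the case for the split does not depend on it.

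A reader might go further and infer that the coder must guess, that guesses will lean towards approval, and that the balance between acceptable and unacceptable uses will shift by a definite number of points. The Protocol does not support this. It states no coding rule that compels a guess, gives no error rate or direction of error, and defines no such balance as an endpoint.

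**Conclusion.** The point holds in limited form. As shown, 5D merges two opposite questions, and answers that list situations without a direction cannot be reliably assigned to either side. The manual check would not expose wrong assignments, because it rereads the same words. Answers that state a direction are unaffected.

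The conclusion rests on two conditions: that the form offers one field for 5D, and that some respondents answer with an undirected list. The number of such answers is unknown, and the illustrative counts must not be read as an estimate. The item is one of ten opinion questions (4A to 4E and 5A to 5E) in a descriptive survey, with no hypothesis test or stated sample size depending on it. The point is therefore a worthwhile improvement to the instrument and does not threaten the study as a whole. It is best settled before the distribution planned for May 2026, because later coding decisions cannot supply the missing direction.

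**What to change.** Replace 5D with two free-text fields, for example *In what situations should AI be used in healthcare?* and *In what situations should AI not be used?* Take the direction of each answer from the field in which it was written, and have the language models and the human reviewers code themes within that field.

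The cost is one additional free-text field in each language, slightly more respondent time on a questionnaire stated to take 15 to 20 minutes, and a brief re-check of the French and English wording, because the tested instrument changes. If the REDCap form already separates the two directions, it is enough to show this in the appended questionnaire.
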